- Amount of total daily insulin doses (units) utilized per day during therapy among patients with type 2 diabetes, compared between treatment arms and to a prior to enrollment outpatient insulin regimen
- serum potassium covariate adjusted for baseline with attention to both elevation and depression

Single-Center Exploratory Outcomes at Vanderbilt University Medical Center

The following exploratory outcomes will only be performed in patients at Vanderbilt University Medical Center who elect to participate in a sub-study. Patients can decline to participate in this sub-study and still participate in parent clinical trial. To explore changes in the plasma proteome during IV diuresis, we will collect one 15mL blood sample (10mL in purple top EDTA tube and 5mL in red top tube) at baseline and on the final study day (Day 5 or discharge).

2.4 Safety Outcomes: Compared between treatment arms during the index stay from signing of informed consent to hospital discharge

- Change in the estimated Glomerular Filtration Rate by the MDRD equation at discharge adjusted for baseline
- Incidence of ketoacidosis, identified by the study team as elevated ketones in the urine and an arterial blood pH < 7.35 and adjudicated by the Clincal Events Committee
- Serum glucose covariate adjusted for baseline with attention to both elevation (> 400mg/dl) and depression (< 70mg/dl)
- Potential prolonged hospitalization as a result of hypoglycemia requiring medical intervention as adjudicated by the Clinical Events Committee
- Potential prolongation of hospitalization as a result of incidence of hypovolemic hypotension, defined as a symptomatic hypotension with a sustained systolic blood pressure less than 90 mmHg over 30 minutes and requiring medical intervention as adjudicated by the Clinical Events Committee. All hypotension episodes requiring medical intervention will be evaluated by the Clinical Events Committee.
- Inpatient mortality

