5.4 Clinical Event Committee

The CEC will consist of 3 independent clinicians, which will consist of at least one endocrinologist and at least one heart failure specialist. The members of this committee

will be independent of the study implementation teams and will be blinded to study arm assignment. This committee will review abstracted clinical data to determine when primary endpoints and major events have occurred. The CEC will review data for the following study outcomes:

- Potential inhospital worsening heart failure events identified by the following criteria:
 - New intravenous inotropic therapy
 - New admission to an intensive care unit
 - New non-invasive positive pressure ventilation with bilevel positive airway pressure
 - 2 or more increases in IV diuretic protocol intensity after Study Day 1
- 30-day readmission events for heart failure or diabetes-related care
- Prolonged hospitalization as a result of the following safety outcomes: hypotension requiring medical intervention or hypoglycemia requiring medical intervention
- In-hospital incidence of ketoacidosis
- Inpatient mortality for causality

All criteria and definitions will be pre-specified in detail in the Clinical Events Committee Charter. Only outcomes adjudicated as such by the Clinical Events Committee will be considered. If there are valid reasons for questioning an adjudication, such as an inexplicable outlier during analysis, the Principal Investigator may formally request a review of the case. In such situations, the Clinical Events Committee has final determination.

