 - a. Repeated as per doubling of the cumulative Day 2 loop diuretic dose (log2 cumulative loop diuretic dose centered at 40mg)
- d) Spot urine sodium-based diuretic efficiency defined as the spot urine sodium concentration (mmol/L) on Day 2 per 40mg of IV furosemide equivalents (preceding loop diuretic dose)
- e) Fractional excretion of sodium (FENa)-based diuretic efficiency on Day 2 of IV therapy defined as the FENa from a spot urine test on Day 2 of IV therapy collected ~2 hours after bolus loop dose per 40 mg of IV furosemide equivalents.
 - a. Repeat as per doubling of the cumulative loop diuretic dose (log2 cumulative loop diuretic dose centered at 40mg)
- f) Urinary Na/K ratio at Day 2 of IV therapy adjusted for baseline.
- g) Calculated 6-hour sodium output on Day 2 of IV therapy using spot urine sodium collected 2 hours after bolus loop dose.
- h) Length of hospital stay, measured as days from admission to discharge
- i) Presence of symptoms of congestion and dyspnea at discharge, measured via blinded-physician exam and patient reported congestion scores.
- j) Hospital readmission within 30 days of discharge for any cause.
- k) Number of days at home without hospitalization or emergency room visit during 30-day follow up period.
- 1) Mean serum glucose during therapy
- m) Amount of total daily insulin doses (units) utilized per day during therapy, compared between treatment arms and to a "prior to enrollment" outpatient insulin regimen.
- n) Analyze the change in basic metabolic panel laboratory values and hemoglobin from baseline to end of study
- o) Serum potassium covariate with attention to both elevation and depression.

Hypokalemia levels are defined as

- a. Not hypokalemic: serum potassium > 3.4 mEq/L
- b. Mild: serum potassium 3.0 3.4 mEq/L
- c. Mod-Severe: serum potassium < 3.0 mEq/L

Hyperkalemia levels are defined as

- a. Not hyperkalemic: serum potassium < 5.1 mEq/L
- b. Mild: serum potassium 5.1 5.5 mEq/L
- c. Severe: serum potassium > 5.5 mEq/L

Safety Endpoints: Comparing differences among the two arms in the following:

- a) Estimated Glomerular Filtration Rate by the MDRD equation at discharge adjusted for baseline. A sensitivity analysis of eGFR by the CKD-EPI equation will also be done.
- b) Incidence of ketoacidosis as adjudicated by the CEC
- c) Serum glucose with attention to both elevation and depression.
 - a. Hypoglycemia is defined as:
 - i. Not hypoglycemic: serum glucose > 70 mg/dl

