 - ii. Mild: serum glucose 54-69 mg/dl
 - iii. Mod-Severe: serum glucose < 54 mg/dl
 - b. Hyperglycemia is defined as:
 - a. Not hyperglycemic: serum glucose < 200 mg/dl
 - b. Mild: serum glucose 200-300 mg/dl
 - c. Severe: serum glucose > 300 mg/dl
- d) Incidence of hypovolemic hypotension, defined as symptomatic hypotension with a sustained systolic blood pressure less than 90 mmHg lasting at least 30 minutes requiring fluid administration.
- e) Inpatient mortality

Design Considerations

Randomization

Patients will be randomized in a 1:1 ratio to receive either intervention or structured usual care. Randomization will use block randomization stratified by site with block sizes of 4.

Power and Sample Size

We anticipate dapagliflozin will increase the weight loss while decreasing the cumulative furosemide dose required to achieve euvolemia. On the basis of the historical literature, we project an increase in diuretic efficiency by 0.1kg/40mg IV furosemide in the Dapagliflozin arm to be a clinically meaningful difference. We project that our diuretic protocol will decrease variations in loop diuretic dosing, which drive large standard deviations. We project a normally distributed standard deviation within each arm to be 0.25kg/40mg. A sample size of 120 experimental subjects and 120 control subjects will have 87% power to detect a probability of 0.611 that an observation in the Dapagliflozin arm is less than an observation in the structured usual care arm using a Wilcoxon (Mann-Whitney) rank-sum test with a 0.05 two-sided significance level.

Statistical Approach

Descriptive Analysis

Initially, we will describe the study cohort pooled across all sites, both overall and grouped by treatment assignment. To characterize the study sample, demographic, clinical, and lab data will be described overall and by treatment arm. Categorical variables will be described using frequencies and proportions; continuous variables will be described using means and standard deviations as well as medians and interquartile ranges (IQR). Missingness will be recorded for each variable. To further assess the distribution of variables, graphical summaries will be displayed using graphs such as box-plots, dot-plots,

violin-plots, and/or histograms. No statistical testing will be done to compare characteristics across groups. At a minimum, the following baseline variables will be described:

- Age (years)
- Sex

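### Protocol and SAP define the hypotension safety outcome in two ways, and committee-adjudicated prolonged stay from hypoglycaemia has no SAP analysis

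*SAP*

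**What the plan says.** **Hypotension.** SAP Safety Endpoints d) counts symptomatic hypotension with systolic pressure "less than 90 mmHg lasting at least 30 minutes requiring fluid administration". SAP Safety Analyses d) compares its incidence between arms with a Pearson chi-square test. Neither entry mentions the Clinical Events Committee or length of stay. The safety endpoints in the protocol's Clinical Trial Summary use the same fluid-based wording, also without the committee. Protocol 7.4 defines hypovolemic hypotension as the fluid-requiring subset of hypotension.

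Protocol 2.4 is different. Its outcome is potential prolongation of the stay from hypovolemic hypotension "requiring medical intervention as adjudicated by the Clinical Events Committee", and it adds: "All hypotension episodes requiring medical intervention will be evaluated by the Clinical Events Committee". The committee list in the Clinical Trial Summary and protocol 5.4 name prolonged hospitalization from hypotension needing medical intervention. Section 5.4 sets the general rule: "Only outcomes adjudicated as such by the Clinical Events Committee will be considered".

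**Hypoglycaemia.** Protocol 2.4 lists as a safety outcome "Potential prolonged hospitalization as a result of hypoglycemia requiring medical intervention as adjudicated by the Clinical Events Committee". The synopsis committee list and 5.4 repeat it. SAP Safety Endpoints c) and Safety Analyses c) cover serum glucose only: daily values and glycemic status by arm. The top hypoglycaemia category is "Not hypoglycemic: serum glucose > 70 mg/dl", followed by mild at 54-69 and moderate-severe below 54 mg/dl. The protocol's threshold for a depressed glucose is below 70 mg/dl.

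**The concern.** Protocol 2.1 says that, even if the primary endpoint is missed, the trial would be worthwhile for establishing the safety of starting dapagliflozin in hospital, and it names hemodynamic and glycemic outcomes among those meant to show this. Hypotension and hypoglycaemia are such outcomes. The trial is open-label, and blinded adjudication is the protection the protocol provides for these events.

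With two definitions in force, the hypotension result can depend on which document the analyst follows, and that choice could be made after the data are seen. With no planned analysis, an adjudicated hypoglycaemia outcome could go unreported by arm without anyone having decided to drop it. The protocol does not fill the gap: section 10.0 refers to the SAP for full methods.

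**Working it through.** No power or sample-size figure enters here. The check compares the texts and enumerates the glucose cut-points.

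**Step 1: hypotension, side by side**

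| Place | Event | Intervention | Prolonged stay needed | Committee named |
|---|---|---|---|---|
| Protocol synopsis, safety endpoints | symptomatic hypovolemic hypotension, incidence | fluid | no | no |
| Protocol 7.4 (adverse events) | hypovolemic subset of hypotension | fluid | no | no |
| SAP Safety Endpoints d) and Safety Analyses d) | symptomatic hypovolemic hypotension, incidence | fluid | no | no |
| Protocol 2.4 | symptomatic hypovolemic hypotension | medical intervention | yes (potential) | yes |
| Protocol synopsis, committee list | hypotension | medical intervention | yes | yes |
| Protocol 5.4 | hypotension | medical intervention | yes | yes |

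Protocol 7.4 also lists prolonged hospitalization from hypotension or hypoglycaemia as a separate reportable event, so both versions appear in that section.

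**Step 2: which episodes count under each version**

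- Symptomatic, sustained, fluid-treated, stay prolonged: counts under both.
- The same episode without prolongation: counts under the SAP and synopsis endpoint, but is not a prolonged-stay outcome. Under 2.4 the committee would still review it, since 7.4 treats fluid boluses as an intervention.
- Treated only with a vasopressor or inotrope, stay prolonged: not in the SAP endpoint. It fits the wording of 5.4 and the synopsis committee list. Whether it fits 2.4 is arguable, because 2.4 says hypovolemic.

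The second pattern alone shows that the two versions are not interchangeable.

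**Step 3: where the SAP names the committee**

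The SAP names the committee for worsening heart failure, for 30-day readmission for heart failure or diabetic reasons, and for ketoacidosis. Ketoacidosis is the only safety endpoint where it does so. Hypotension carries no such phrase.

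**Step 4: hypoglycaemia**

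Protocol 2.4 has two separate entries: serum glucose with attention to high and low values, and adjudicated prolonged stay from hypoglycaemia. The SAP's glucose endpoint corresponds to the first. Nothing in SAP Safety Endpoints a) to e) or Safety Analyses a) to e) corresponds to the second. The SAP's version table records new hypoglycaemia severity categories but no removal of an adjudicated outcome.

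**Step 5: glucose categories**

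Each value g from 20 to 800 mg/dl was tested against the SAP rules: g > 70, 54 ≤ g ≤ 69, g < 54.

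- Whole numbers: exactly one value, 70, falls in no category.
- Steps of 0.1: the ten values from 69.1 to 70.0 fall in none.
- Hyperglycaemia rules (< 200, 200-300, > 300), whole numbers: no gap and no overlap.
- With g ≥ 70, 54 ≤ g < 70 and g < 54, every value in steps of 0.1 falls in exactly one category.

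**The case against.** The strongest reply is that the SAP did not depart from the protocol on hypotension. A reader might infer that the statisticians substituted a new endpoint. The documents do not support that: the SAP wording matches the protocol synopsis and fits the definition in 7.4, so the conflict is already inside the protocol. This stands, and it makes the point one of reconciliation.

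A reader might also infer that the SAP analyses investigator-reported events and leaves the blinded adjudications unused. That rests only on silence. Protocol 2.4 sends every hypotension episode needing intervention to the committee, 5.4 says only adjudicated outcomes count, and nothing in the SAP sets that rule aside. The SAP is equally silent on the committee for inpatient mortality, which 5.4 assigns to it for causality. Detailed criteria are placed in a committee charter that is not among these documents. Because the SAP does name the committee for ketoacidosis, its silence on hypotension still needs clearing up.

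On hypoglycaemia, it is fair to answer that laboratory glucose is compared by arm, length of stay is compared, and the event is collected as an adverse event under 7.4, with adverse event reports going to the monitoring board. All of that is true, and it would be wrong to say hypoglycaemia is not analysed. None of it is a by-arm analysis of the adjudicated outcome listed in 2.4.

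The 70 mg/dl gap gains or loses no hypoglycaemia event for whole-number values, since both low categories are unaffected.

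Finally, incidence is arguably a more sensitive safety measure than prolonged stay, which needs a further causal judgement. The documents give no ground for ranking one above the other.

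**Conclusion.** The point holds as an inconsistency between documents with one omission. Hypotension has two conflicting definitions, which differ in the qualifying intervention, in whether the stay must be prolonged, and in whether the committee is named. Adjudicated prolonged stay from hypoglycaemia is a listed safety outcome with no SAP endpoint or analysis. The unclassified value of 70 mg/dl is a minor boundary error.

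The effect on the safety results cannot be computed, because the documents give no rates for hypotension, hypoglycaemia or prolonged stay. The conclusion assumes that the committee charter, which cannot be seen here, does not already settle the hypotension definition, and that no other analysis document covers the hypoglycaemia outcome. It should be corrected before analysis; it does not touch the primary endpoint.

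**What to change.** 1. Reconcile the hypotension definition in the protocol synopsis (safety endpoints and committee list), protocol 2.4, 5.4 and 7.4, and SAP Safety Endpoints d) and Safety Analyses d). Which clinical definition to adopt is for the investigators.
2. State in the SAP that the hypotension events analysed are those confirmed by the blinded committee. Report by arm both the incidence of adjudicated episodes and adjudicated prolonged stay, without ranking one above the other.
3. Add adjudicated prolonged stay from hypoglycaemia needing medical intervention to the SAP safety endpoints and analyses, beside the laboratory glucose analysis.
4. Set the SAP's not-hypoglycemic category to 70 mg/dl or above, to match the protocol's cut of below 70. Writing the mild category as 54 to below 70 also closes the gap for any decimal values.

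The cost is SAP wording, matching protocol text and a few extra rows in the safety table. The committee reviews needed are ones the protocol already requires.

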	Day 5 or Discharge: standing weight, NT-proBNP, BMP, vital signs, urine output quantification, document HF and diabetic medications, congestion score, outcomes assessment, remind primary team to schedule standard-of-care 3-7-day follow-up visit with endocrinology (if patient has diabetes) and HF			
	30-day phone follow-up : document HF and diabetic medications, outcomes assessment			
Study Duration	Enrollment is anticipated to occur over 14 months with the end of study occurring at hospital discharge and a 30-day phone-call follow-up			
Clinical Event Committee	The following events will be adjudicated by a Clinical Event Committee blinded to patient assignment:			
	 Worsening heart failure defined as inpatient administration of an IV inotrope with dobutamine, milrinone, or dopamine, new admission to an intensive care unit, new non-invasive positive pressure ventilation with bilevel positive airway pressure, or increase in the IV diuretic protocol intensity by 2 rows after Study Day 1 30-day hospital readmissions due to heart failure or diabetes- related events 			

	 Prolonged hospitalization as a result of hypoglycemia requiring medical intervention Prolonged hospitalization as a result of hypotension requiring medical intervention In-hospital incidence of ketoacidosis Inpatient mortality
Data and Safety Monitoring Board	An independent Data and Safety Monitoring Board will advise the principal investigator on safety aspects and overall progress of the study.

Table of Contents:

- **1.0** Background and rationale
- 2.0 Study outcomes
- 3.0 Inclusion/Exclusion criteria
- 4.0 Patient screening, consent, and randomization
- 5.0 Study Procedures
- 6.0 Risks
- 7.0 Reporting of adverse events
- 8.0 Data collection and record keeping
- 9.0 Study withdrawal
- 10.0 Statistical methods
- 11.0 References

1.0 Background and Rationale:

Patients with acute decompensated HF (ADHF) are generally admitted due to symptoms of congestion and 90% are treated with a loop diuretic.¹ However at least one-third of these patients are inadequately decongested due primarily to "diuretic resistance" and/ or "cardiorenal syndrome".^{2,3} The inability to achieve decongestion is associated with a worse prognosis and a higher rate of re-hospitalization for ADHF.² More than 40% of all patients admitted with ADHF have diabetes and that percentage is growing both in Heart Failure with Reduced Ejection Fraction (HFrEF) and Preserved Ejection Fraction (HFpEF).⁴

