3.0 Inclusion/Exclusion criteria

- Inclusion Criteria
 - Age of 18 years or older
 - Randomized within 24 hours of presentation during a hospital admission for hypervolemic decompensated heart failure defined as either:
 - pulmonary artery catheterization with a pulmonary capillary wedge pressure greater than 19mmHg plus a systemic physical exam finding of hypervolemia (peripheral edema, ascites, or rales on auscultation)
 - in the absence of pulmonary artery catheterization data 2 of the following signs or symptoms: peripheral edema, ascites, jugular venous pressure > 10mmHg, orthopnea, paroxysmal nocturnal dyspnea, 5-pound weight gain, or signs of congestion on chest x-ray or lung ultrasound

- Standard-of-care monitoring on an inpatient ward and standard-of-care basic metabolic panel laboratory assessment once daily during the study period
- Planned or current use of IV loop diuretic therapy during current hospitalization
- eGFR \geq 25 ml/min/1.73m² by the MDRD equation
- Exclusion Criteria
 - Type 1 diabetes
 - Serum glucose < 80mg/dl at enrollment
 - Systolic blood pressure < 90mmHg at enrollment
 - Requirement of intravenous inotropic therapy at enrollment or anticipated need of therapy during the study period
 - History of hypersensitivity to any SGLT2 inhibitors
 - Women who are pregnant or breastfeeding
 - Severe anemia (Hemoglobin < 7.5g/dl)
 - Severe uncorrected aortic or mitral stenosis
 - Inability to perform standing weights or measure urine output accurately
 - History of diabetic ketoacidosis
 - Chronic combination nephron blockade with loop and thiazide therapy as an outpatient scheduled daily for more than 7 days prior to admission (Does not include HCTZ < 50mg for blood pressure)
 - Diffuse anasarca with 4+ edema and projected hypervolemia exceeding 40-pounds
 - Severe hepatic impairment (Child-Pugh class C if hepatic impairment is in question)
 - Clinical picture consistent with acute myocardial infarction including troponin rise and fall or ischemic changes on electrocardiogram
 - Site investigator determines the subject is not a good candidate to participate in study at this time

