4.0 Patient screening, consent, and randomization

We will perform a randomized, open-label, multicenter trial to investigate the safety and clinical effects of initiating dapagliflozin vs standard of care in patients admitted to the hospital with ADHF with protocolized diuretic therapy in both treatment arms.

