4.3 Randomization

Randomization will occur during the hospitalization within 24 hours of evaluation of AHF. Enrollment and randomization will be accomplished by study personnel logging into REDCap, confirming the inclusion and exclusion criteria have been satisfied, and using the REDCap randomization engine. Participants will then be randomized to either dapagliflozin or standard-of-care and will be registered as *randomized*.

[figure not shown]

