Inpatient and 30-day endpoints of interest will be summarized overall and by treatment assignment. Categorical variables will be described using frequencies and proportions; continuous variables will be described using means and standard deviations as well as medians and interquartile ranges (IQR). Missingness will be recorded for each variable. For those endpoints that are a composite of multiple endpoints, such as incidence of worsening heart failure (requiring IV inotropic therapy, new admission to an ICU, new non-invasive positive pressure ventilation with bi-level positive airway pressure, or increase in the IV diuretic protocol intensity by 2 rows after Day 1 as adjudicated by the CEC) and hospital readmission within 30 days of index hospitalization discharge (for heart failure-related reasons or diabetic reasons), frequencies will be summarized overall and for each level.

No statistical testing will be done to compare characteristics across groups.

Main Analysis

All model results (unadjusted and adjusted) will be summarized with point estimates, 95% confidence intervals (CIs), and p-values displayed in tabular form or graphically, along with appropriate model fit statistics. Missingness in adjusting covariates will be addressed using multiple imputation based on predictive mean matching.

Primary Analysis: Our main analysis will be a covariate-adjusted proportional odds (PO) regression model with our outcome being cumulative change in weight per 40mg of IV furosemide equivalents from

enrollment to the minimum of Day 5 or discharge and the main predictor being treatment assignment. Adjusting covariates will be pre-specified and include baseline weight. Baseline weight will be fit with restricted cubic splines with 3 knots to relax the linearity assumptions.

Secondary Analyses:

Appropriate model diagnostics will be run to assess model fit. If model diagnostics suggest the planned approach violates necessary assumptions, alternative methods will be pursued.

- a) Binary logistic regression will be used to assess the association of the incidence of worsening heart failure as adjudicated by the CEC with treatment assignment.

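### A single block size of 4 within site, in an open-label trial, makes on average one third of allocations deducible by staff who know or infer it

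*SAP*

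**What the plan says.** The SAP (Design Considerations, Randomization) sets the allocation ratio, "Patients will be randomized in a 1:1 ratio to receive either intervention or structured usual care", and the method: "Randomization will use block randomization stratified by site with block sizes of 4". Site is the only stratum and 4 the only block size.

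Protocol 4.0 describes the design: "We will perform a randomized, open-label, multicenter trial". Under Protocol 4.3, study personnel randomize in REDCap after "confirming the inclusion and exclusion criteria have been satisfied, and using the REDCap randomization engine". That section gives no block size. Neither document says that sizes vary or that the size is kept from sites.

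Three other provisions bear on the point:

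- Protocol 3.0 has a judgment exclusion: "Site investigator determines the subject is not a good candidate to participate in study at this time".
- Protocol 3.0 limits timing: "Randomized within 24 hours of presentation during a hospital admission for hypervolemic decompensated heart failure".
- The SAP's primary analysis names one covariate: "Adjusting covariates will be pre-specified and include baseline weight".

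**The concern.** REDCap hides the list until eligibility is confirmed. It does not stop staff from working out the next allocation from earlier ones at the same site, because treatment is open and every block of 4 holds two of each arm.

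Selection bias needs a decision made after the next allocation is known and before the patient is randomized. The judgment exclusion is such a decision. Holding a patient back for a later slot is largely closed off by the 24-hour window and the slow pace per site, so the remaining route is mainly declining to enrol.

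If staff took that route, patients accepted into known dapagliflozin slots could differ in prognosis from those accepted into known control slots. Adjusting for baseline weight alone would not remove a difference in, say, renal function or natriuretic peptide level.

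**Working it through.** **Inputs.** From the SAP: 1:1 ratio, block size 4, strata by site, SD 0.25 kg/40 mg, target difference 0.1 kg/40 mg, 120 per arm, two-sided 0.05. From the Protocol summary: 240 patients, up to six sites, 14 months of enrolment. Equal enrolment across six sites is an assumption.

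**The plan's own figure.** The documents give no figure for predictability. The nearest stated figure is 87% power. SE = 0.25 × √(2/120) = 0.0323, 0.1/0.0323 = 3.10, and Φ(3.10 − 1.96) = 0.87. This agrees, and it does not depend on block size.

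**Certain allocations.** A 1:1 block of 4 has 6 equally likely sequences. An allocation is certain once one arm's two places are used.

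| Position | Probability that the allocation is certain | Best-guess success |
|---|---|---|
| 1 | 0 | 1/2 |
| 2 | 0 | 2/3 |
| 3 | 1/3 | 2/3 |
| 4 | 1 | 1 |

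- Expected certain slots per block: 1/3 + 1 = 4/3, which is 33.3% of 4. A single block has either 1 or 2 certain slots.
- Over 60 complete blocks: 60 × 4/3 = 80 of 240 (SD about 3.7).
- A site that stops 1, 2 or 3 patients into a block loses 0.33, 0.67 or 0.67 expected certain slots relative to n/3. Six sites lose at most 6 × 0.67 = 4, so the expected total is 76 to 80.
- Best-guess success: (1/2 + 2/3 + 2/3 + 1)/4 = 70.8%, against 50% by chance.

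**Alternatives.** The mixed-size rows come from simulation (3,000 sites of 40 patients), with each size equally likely and an observer who knows the set of sizes but not the size of each block.

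| Scheme | Certain | Best guess |
|---|---|---|
| Fixed 4 | 33.3% | 70.8% |
| Fixed 6 | 25.0% | 68.3% |
| Fixed 8 | 20.0% | 66.6% |
| Random 4, 6 | about 5.5% | about 69% |
| Random 4, 6, 8 | about 2.3% | about 68% |

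**Can staff wait for a better slot?** 240/6/14 = 2.9 patients per site per month, or one every 10 to 11 days. Against a 24-hour window, waiting is seldom possible.

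**Illustrative bias (assumptions, not from the documents).** Suppose staff decline a fraction f of poor-prognosis patients (the worse half, as they judge it) before known dapagliflozin slots, and the same fraction of good-prognosis patients before known control slots. Let r be the correlation between their judgment and the endpoint. One third of each arm sits in known slots, and the mean of the better half of a standard normal is 0.798. So

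bias = 2 × (1/3) × r × 0.25 × 0.798 × f/(2 − f).

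| f | Bias, r = 0.3 to 0.5 (kg/40 mg) | Two-sided type I error |
|---|---|---|
| 0.1 | 0.002 to 0.003 | 5.0% to 5.1% |
| 0.2 | 0.004 to 0.007 | 5.2% to 5.6% |
| 0.3 | 0.007 to 0.012 | 5.6% to 6.5% |
| 0.5 | 0.013 to 0.022 | 7.0% to 10.6% |

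At f = 0.5 and r = 0.5 the bias is 2/3 × 0.5 × 0.25 × 0.798 × 0.333 = 0.022, which is 0.69 SE and 22% of the target. If only one of six equal sites behaved this way, it would be 0.022/6, about 0.004. The formula counts certain slots only, not action on better-than-chance guesses.

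**The case against.** Site-stratified permuted blocks of 4 are a valid design and break no rule in the plan. Harm needs a chain of events: staff know or infer the size, track every allocation, act on it, and judge prognosis well enough to matter. The documents show none of these. The block size stands only in the SAP, whose first approval (10.2021) follows Protocol version 4.0 (9.21.2021), and site staff work from the Protocol. Most eligibility criteria are measured values. Baseline weight, eGFR and NT-proBNP are to be described by arm, so gross selection would be visible. The bias figures rest on assumed inputs, and most of the grid lies near 5%. Varied blocks barely lower best-guess success.

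Much of this stands. It is right that exploitation is unproven, that 10.6% is an extreme corner, and that varied sizes mainly remove certainty, which is why withholding the sizes matters as well. It does not close the opening. Not printing the size in the Protocol is not the same as withholding it, and a repeated two-and-two balance can be inferred from a site's own sequence. Tables of baseline values by arm may reveal a gross imbalance, but they neither prevent selection nor use the predicted allocation, where selection would show most clearly.

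**Conclusion.** The concern holds as an avoidable design weakness, not as evidence of bias. On the text, one fixed block size of 4 is used within site in an open-label trial, with a judgment exclusion before allocation and no statement that the size is varied or concealed. If the size is known or inferred and all allocations are tracked, an average of 33.3% of allocations (76 to 80 of 240) are certain and 70.8% can be guessed correctly.

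The effect on the primary result depends on behaviour that the documents do not describe. Across the assumed range it runs from negligible (2% of the target difference) to material (22% of the target, type I error about 10.6%), and the upper end needs strong selection in every deducible slot at every site. Sample size and the stated power are not affected. The change is worth making because it is cheap. Confidence is medium, since the documents do not show what sites knew.

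**What to change.** Replace the fixed size with randomly varied block sizes within site, for example 4, 6 and 8. Keep the sizes in a restricted randomization document that sites cannot see, and say in the SAP that this was done.

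- **If enrolment is under way:** replace the remaining REDCap lists at the next block boundary in each site. The documents do not say whether REDCap allows this, so it needs confirming.
- **If enrolment has ended** (the SAP's latest version is dated 3.2023 and enrolment dates are not given): state whether sites knew the block size. Then compute each patient's probability of dapagliflozin just before allocation from the earlier allocations in the block (0, 1/3, 1/2, 2/3 or 1), and test whether baseline weight, eGFR and NT-proBNP are related to it. The check can detect selection only on what was measured.

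The cost is a regenerated allocation table. The largest possible imbalance within a site rises from 2 to 4 patients. At a 40-patient site the mean absolute difference would be about 0.55 patients, against 0 with complete blocks of 4. The retrospective check uses data already collected.
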